5. STUDY PARAMETERS/ DATA COLLECTION

Data may be extracted from UH patient medical records by UH research-credentialed (CREC/CITI-certified) or UH employees and recorded onto UH Radiology password-protected computers. Data will be collected and stored in REDCap or in a password protected folder on the secured UH s:drive in order to correlate image findings with patient progress/care. Data will include the following:

- Name
- MRN
- Age
- Email
- Phone number
- Date of last menstrual period
- Date of biopsy
- Biopsy results
- TNM status/cancer stage
- Pathology report with hormone receptor status
- MammaPrint score
- Chemotherapy schedule and treatment regime
- Date of surgery
- Type of surgery (mastectomy or breast conserving surgery)
- Final surgical pathology
- MRI images

6. STATISTICAL CONSIDERATIONS

1. From the 3D MR Fingerprinting maps, T1 and T2 relaxation times will be obtained for tumor, and peritumoral and normal breast tissue at all three scans.
2. From routine MRI scans, the tumor size and tumor ADC will be obtained.
3. Changes in all quantitative measurements will be compared between responders and non-responders based on final surgical pathology and the predictive value of 3D MR Fingerprinting as compared to existing techniques would be assessed using appropriate t-tests and logistic regression analysis.

Sample Size Calculation: Based on our pilot data, we expect a 25% change in T1 and T2 relaxation times in responders and less than 7% change in non-responders with an effect size of 18% (0.18). At a significance level of 0.05 and power of 80%, the expected sample size is 62. Based on our pilot data, we also expect an attrition and drop-out rate of 50%, and thus total number of subjects recruited will be 124.

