On the other hand, T1 and T2 relaxation times represent intrinsic tissue properties in MRI. Relaxometry, i.e. measurement of T1 and T2 relaxation times can also provide objective and reproducible information about pathology. Older studies showed that relaxation times differed between healthy breast tissue and breast cancers^{11,12} and could potentially be used to predict early response to chemotherapy¹³⁻¹⁵. However, relaxometry as a response assessment technique has not yet crossed the translational gap because it is technically difficult in breast and there is very limited evidence on breast relaxometry for response assessment. We developed a novel 3D Breast

Magnetic Resonance Fingerprinting (3D MRF) technique, which allows simultaneous estimation of both T1 and T2 relaxation times in a clinically feasible manner and in less than 6 minutes of scan time¹⁶. This is a volumetric acquisition technique that generates co-registered quantitative maps to characterize breast tumor and peritumoral and contralateral breast tissue.

[figure not shown]
2. Preliminary Studies:

Our preliminary work on 3D breast MRF has shown that there are significant differences in T1 and T2 relaxation times between tumor and normal breast tissue^{16, 17}. We scanned 12 women with biopsy proven breast cancer and the tumor T1 and T2 relaxation were longer compared to normal breast tissue (mean \pm SD, Tumor T1: 1156 ± 200 ms, Normal breast T1: 846 ± 388 ms, Tumor T2: 72 ± 14 ms, Normal breast T2: 48 ± 12 ms, $p = 0.039$ for T1, $p < 0.001$ for T2). In addition, we performed a repeat 3D MRF scan after one cycle of chemotherapy in 7 patients and patients with decrease in tumor size showed significant decrease in tumor T1 and T2 relaxation times while non-responders showed only a negligible change in tumor T1 and T2 relaxation times¹⁷ (Table 1). Figure 1 shows representative 3D breast MRF maps from one patient who was scanned before and after one cycle of chemotherapy. Thus we hypothesize that 3D MRF before, during and after chemotherapy can provide additional quantitative information about changes during treatment and may predict early response to chemotherapy.

Table 1: Pilot data showing greater % decrease in T1 and T2 relaxation times in patients showing treatment response after one cycle of chemotherapy compared to non-responders

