If the patient is not scheduled for a clinical scan within 1 month of end of chemotherapy treatment, we will contact the patient to schedule a research only 3D MR Fingerprinting scan. Breast cancer is hard to visualize on MRI post treatment, so we would like to administer IV gadolinium contrast for research purposes. Patients will be reconsented prior to the research only scan to determine whether or not they will receive IV contrast. If the patient declines

administration of contrast for the post treatment scan, we will perform a non-contrast scan. Acquisition of images will take 30-45 minutes.

Criteria for response assessment

Final surgicopathology results would be used for response assessment. Thus pathology reports with pT0N0 would be designated as pathological complete response while pT0 but with residual nodal deposits on pathology would be considered as primary tumor response for analysis purpose. Presence of any residual tumor on pathology would be considered as non-responder.

In the sub-group of patients who fail to undergo surgery at the end of treatment due to reasons beyond the control of study researchers, RECIST version 1.1 criteria would be considered as surrogate criteria for response (1). Thus no visible tumor and nodes at end of treatment scan will be considered complete response, >30% decrease in long-axis diameter (LAD) compared to baseline will be partial response, > 20% increase in LAD will be progressive disease while < 30% decrease/ > 20% increase in LAD will be considered stable disease.

All categories of response would be considered independently for analysis.

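### The 0.18 in the sample-size paragraph is a raw gap between mean percentage changes, not an effect size for the planned t-test, so 80% power with 62 patients is not shown

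*Combined protocol and SAP*

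**What the plan says.** Section 6 (Statistical Considerations) states the expectation that "we expect a 25% change in T1 and T2 relaxation times in responders and less than 7% change in non-responders". The sample-size sentence continues "with an effect size of 18% (0.18). At a significance level of 0.05 and power of 80%, the expected sample size is 62". A 50% attrition allowance follows, and "thus total number of subjects recruited will be 124".

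Item 3 of the same section gives the comparison to be made: "Changes in all quantitative measurements will be compared between responders and non-responders based on final surgical pathology", using t-tests and logistic regression.

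Section 6 credits its expectations to pilot data. Section 2 (Preliminary Studies) says "we performed a repeat 3D MRF scan after one cycle of chemotherapy in 7 patients", and that "patients with decrease in tumor size showed significant decrease in tumor T1 and T2 relaxation times". The title of Table 1 in Section 2 refers to "patients showing treatment response after one cycle of chemotherapy compared to non-responders". For the trial itself, the response criteria in Section 4.4.2 are pathological: "Presence of any residual tumor on pathology would be considered as non-responder".

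**The concern.** For a t-test on changes, an effect size is the difference in mean change divided by the SD of change between patients. The paragraph gives this name to the undivided difference. It then states a sample size without an SD, the sidedness, the test or the expected responder share. As worded, the stated effect size cannot lead to 62 for the planned test, and the inputs that could lead there are not given.

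The source of the gap raises a second difficulty. Section 2 describes pilot response by early shrinkage, while the trial counts any residual tumour at surgery as non-response. A patient whose tumour shrinks but persists could therefore be a responder on the pilot's description and a non-responder in the trial. Both the 18-point gap and the ratio of the two groups may differ under the trial's definition.

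This is the only power statement in the text reviewed. As it stands, a reader cannot tell from the paragraph how far 80% depends on the SD and the response rate.

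**Working it through.** **Inputs from Section 6:** expected changes of 25% and (at most) 7%; significance level 0.05; power 80%; 62 patients; 50% attrition; 124 recruited. **Not in the paragraph:** SD of percentage change, sidedness, test, group split. The only SDs in the reviewed text are the tissue values in milliseconds in Section 2, which are not SDs of percentage change. Every SD and split below is therefore an assumption.

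**1. Attrition step.** 62 / (1 − 0.5) = 124. This is correct, and it uses 62 as the evaluable total.

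**2. 0.18 as a standardized difference.** n per group = 2 × ((1.960 + 0.842) / 0.18)² = 484.5, so 485 per group, or 970 in total. With 62 in total (31 per group), power is about 11%. This does not reproduce 62.

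**3. 0.18 as a raw 18-point gap between means.** n per group = 2 × ((1.960 + 0.842) × SD / 18)². At SD 25 this is 30.3, so 31 per group and 62 in total. Any SD from 24.9 to 25.3 gives the same 31. The route suits the planned comparison, but it needs an SD near 25, two-sided testing and equal groups.

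**4. 25% and 7% as two proportions.** Unpooled formula: n per group = (0.25 × 0.75 + 0.07 × 0.93) × (1.960 + 0.842)² / 0.18² = 61.2, so 62 per group. The number matches, but per group: 124 evaluable and 248 recruited at 50% attrition. That conflicts with step 1. The formula also does not suit a mean percentage change, which is not a proportion of patients.

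The reviewed text does not show whether step 3, step 4 or another calculation was used.

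**5. Power of 62 evaluable patients.** Two-sided 0.05, noncentral t, true gap 18 points:

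| Responders : non-responders | SD 15 | SD 20 | SD 25 | SD 30 | Largest SD for 80% |
|---|---|---|---|---|---|
| 31:31 | >99% | 94% | 80% | 64% | 24.9 |
| 19:43 | 99% | 90% | 73% | 57% | 23.0 |
| 16:46 | 98% | 86% | 69% | 53% | 21.8 |
| 12:50 | 96% | 79% | 60% | 45% | 19.7 |

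One-sided testing raises the largest SD at 31:31 to 28.2.

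**6. Other gaps, at SD 25.** A gap of 21 points (25% against 4%) gives 90% at 31:31 and 81% at 16:46. A gap of 15 points gives 64% and 53%.

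**The case against.** The strongest reply is that this is incomplete reporting and not a faulty calculation. Both subtractions and divisions in the paragraph are right, and an ordinary comparison of means gives exactly 62 at an SD of 25. The paragraph rests on pilot data, and the body of Table 1 and Section 3 are missing from the reviewed text. An SD of about 25 there would largely explain the figure. This stands in part. No one can say that the protocol lacks an SD, only that the sample-size paragraph does not state one. A pilot SD would still leave the label wrong and the test, sidedness and split unstated.

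It can also be said that less than 7% in non-responders makes 18 points the smallest gap on the plan's own expectation, so that power could exceed 80%. That is fair, and the 21-point figures show it. The expectation comes from the pilot, however, and the change of response definition could move the gap in either direction.

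Third, a reader might complain that 62 could be total or per group. The paragraph does not label it, but the step to 124 recruited settles it by implication as the evaluable total.

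Two stronger readings are tempting. From the 11%, a reader might infer that the trial is badly underpowered. That follows only if 0.18 is a true standardized difference, and the paragraph shows it to be 25 minus 7. From the two-proportion match, a reader might infer that this formula was used and that 248 patients should be recruited. The match in number is suggestive, but the text does not name the method, and a comparison of means reaches the same number.

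**Conclusion.** The point holds as a labelling error together with unstated inputs. The figure called an effect size is not one for the planned t-test, and 80% power with 62 patients is not shown for the comparison that the trial will make. For an 18-point gap tested two-sided, 62 evaluable patients give at least 80% only if the SD of percentage change is no more than about 25 points with equal groups, or about 22 points at 16:46. Groups are formed by pathology after treatment, so an equal split cannot be set by design, and the reviewed text gives no reason to expect one.

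A shortfall is not proven. At an SD of 15, power is at least 96% at every split tabulated. At an SD of 30, it is at most 64% for an 18-point gap. These results rest on assumed SDs and splits, a common SD in both groups, and 62 patients with evaluable change scores and a response classification.

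**What to change.** Rewrite the sample-size paragraph in Section 6:

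- Remove the effect-size label from 0.18 and call it an 18-point difference in mean percentage change.
- Recompute as a two-sample comparison of mean percentage change. Use the pilot SD, and the gap and responder share expected under the pathology definition in Section 4.4.2.
- State the test and sidedness, and that 62 is the evaluable total.
- Restate the power of 62 in a small table over SD, gap (above and below 18 points) and responder share.

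The cost is one paragraph and one table, and a stated power that may be less favourable than 80%. No change to enrolment is proposed. Whether 124 remains suitable can be judged only after the recalculation.

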7. POTENTIAL RISKS

7.1 Breast MRI

Certain metals are not safe to go into an MRI scanner. Prior to all MRI exams (standard clinical or research), stringent safety checklists will be used to determine if an MRI study can be performed on each patient. All patients will be receiving an MRI exam as part of the standard of care at baseline. This study will add several minutes to the duration of this baseline exam, but will not need any additional administration of contrast agents or drugs.

7.2 MRI Contrast Agent

If the referring physician schedules a standard-of-care MRI exam within 1 month of completion of chemotherapy, MRI contrast agent will not be administered for research purposes.

However, if the referring physician does not schedule a standard-of-care MRI exam within 1 month of completion of chemotherapy treatment (for visit 3), a research only exam will be performed. This exam will include administration of MRI contrast agent unless the subject declines contrast administration. If contrast is administered for research only purposes in this subset of patients, the following risks are present:

Potential risks of IV contrast agents are allergic reaction. Gadolinium-based contrast agents (dyes) may increase the risk of a rare but serious disease called nephrogenic systemic fibrosis in people with poor kidney function with drastically decreased glomerular filtration rate (GFR) below 30ml/min, Chronic kidney disease, CKD 4 and 5). To exclude the risk of Gadolinium induced nephropathy, we will exclude all patients with a GFR below 40 ml/min. This threshold is considerably higher than the current clinical threshold of GFR below 30.

Over 300 million doses of Gadolinium based contrast agents (GBCAs) have been administered since the introduction of these medications in the mid 1980s. The known and

proven adverse effects of these drugs are the possibility of allergic reactions (rare and idiosyncratic), and the development of the extremely rare disease Nephrogenic Systemic Fibrosis (NSF) with the administration of contrast agents in patients with severe renal dysfunction. NSF has been virtually eliminated upon not administering GBCAs in patients with end stage renal disease. Additional precautions such as minimizing use of GBCAs associated with NSF, and elimination of simultaneous administration of double/triple doses of agents, have also contributed. While all GBCAs are known to deposit in neural and other tissues, no harmful effect of this deposition has been documented¹⁸.

7.3 Confidentiality

Finally, there is a risk of a breach of confidentiality. To lower this risk, information will be de-identified by a co-investigator trained in the protection of PHI (Protected Health Information). A unique study code will be assigned to every study subject. This code will be used instead of identifiable information to describe which study subject is which when cases are discussed among study personnel.

8. BENEFITS

There may be no direct health benefits for participation in this study. Participation in this study will help the investigators determine whether these MRI techniques are useful, and may provide benefit to patients undergoing MRI examinations in the future.

9. ALTERNATIVES TO PARTICIPATION

Patients may choose not to participate in this study and clinical care will not be affected.

10. COST TO RESEARCH PARTICIPANTS

The study will pay for all procedures that are directly associated with this research study. Procedures or drugs that are considered standard of care will be the responsibility of the patient and their insurance company.

11. COMPENSATION

Visit 1: Subjects will receive \$100 for research scan

Visit 2: Subjects will receive \$150 for non-contrast research scan

Visit 3: Subjects will receive \$50 for non-contrast research scan or \$100 for contrast research scan

9. ADVERSE EVENTS

An adverse event (AE) is any unfavorable or unintended event, physical or psychological, associated with a research study, which causes harm or injury to a research participant as a result of the participant's involvement in a research study. The event can include abnormal laboratory findings, symptoms, or disease associated with the research study. The event does not necessarily have to have a causal relationship with the research, any risk associated with the research, the research intervention, or the research assessments. Adverse events may be the result of the interventions and interactions used in the research; the collection of identifiable private information in the research; an underlying disease, disorder, or condition of the subject; and/or other circumstances unrelated to the research or any underlying disease, disorder, or condition of

the subject. In general, adverse events that are at least partially the result of (a) or (b) would be considered related to the research, whereas adverse events solely related to (c) or (d) would be considered unrelated to the research.

The significance of an adverse event is used to describe the patient/event outcome or action criteria associated with events that pose a threat to a patient's life or functioning (i.e., moderate, severe or life threatening). Based on the National Cancer Institute Guidelines for the Cancer Therapy Evaluation Program, severity can be defined by the following grades of events:

Grades 1 are mild adverse events. (e.g., minor event requiring no specific medical intervention; asymptomatic laboratory findings only; marginal clinical relevance)

Grades 2 are moderate adverse events (e.g., minimal intervention; local intervention; non-invasive intervention; transfusion; elective interventional radiological procedure; therapeutic endoscopy or operation).

Grades 3 are severe and undesirable adverse events (e.g., significant symptoms requiring hospitalization or invasive intervention; transfusion; elective interventional radiological procedure; therapeutic endoscopy or operation).

Grades 4 are life threatening or disabling adverse events (e.g., complicated by acute, life threatening metabolic or cardiovascular complications such as circulatory failure, hemorrhage, sepsis; life-threatening physiologic consequences; need for intensive care or emergent invasive procedure; emergent interventional radiological procedure, therapeutic endoscopy or operation).

Grades 5 are fatal adverse event resulting in death.

9.1 Serious Adverse Events

A serious adverse event (SAE) is any adverse experience occurring at any dose that results in any of the following outcomes:

1. Results in death.
2. Is a life-threatening adverse experience. The term life-threatening in the definition of serious refers to an adverse event in which the subject was at risk of death at the time of the event. It does not refer to an adverse event that hypothetically might have caused death if it were more severe.
3. Requires inpatient hospitalization or prolongation of existing hospitalization. Any adverse event leading to hospitalization or prolongation of hospitalization will be considered as serious, UNLESS at least one of the following expectations is met:
4. The admission results in a hospital stay of less than 12 hours OR
5. The admission is pre-planned (i.e., elective or scheduled surgery arranged prior to the start of the study) OR
6. The admission is not associated with an adverse event (e.g., social hospitalization for purposes of respite care. However it should be noted that invasive treatment during any hospitalization may fulfill the criteria of "medically important" and as such may be

reportable as a serious adverse event dependent on clinical judgment. In addition where local regulatory authorities specifically require a more stringent definition, the local regulation takes precedent.

7. Results in persistent or significant disability/incapacity. The definition of disability is a substantial disruption of a person's ability to conduct normal life's functions.
8. Is a congenital anomaly/birth defect.
9. Is an important medical event. Important medical events that may not result death, be life-threatening, or require hospitalization may be considered a serious adverse experience when, based upon appropriate medical judgment, they may jeopardize the patient or subject and may require medical or surgical intervention to prevent one of the outcomes listed in this definition. Examples of such medical events include allergic bronchospasm requiring intensive treatment in an emergency room or at home, blood disease or disorders, or convulsions that do not result in inpatient hospitalization, or the development of drug dependency or drug abuse.

9.2 Expectedness

Adverse Events can be Expected or Unexpected.

An expected adverse event is an event previously known or anticipated to result from participation in the research study or any underlying disease, disorder, or condition of the subject. The event is usually listed in the Investigator Brochure, consent form or research protocol.

An unexpected adverse event is an adverse event not previously known or anticipated to result from the research study or any underlying disease, disorder, or condition of the subject.

9.3 Reporting Procedures for All Adverse Events

All participating investigators will assess the occurrence of AEs throughout the subject's participation in the study. Subjects will be followed for AEs for 30 days after biopsy or until death, whichever occurs first. The clinical course of each event will be followed until resolution, stabilization, or until it has been determined that the study treatment or participation is not the cause. The investigator is responsible for ensuring that all adverse events observed by the investigator or reported by the subject which occur after the subject has signed the informed consent are fully recorded in the subject's case report form, subject's medical records, and/or any other institutional requirement. Source documentation must be available to support all adverse events.

A laboratory test abnormality considered clinically relevant (e.g., causing the subject to withdraw from the study), requiring treatment or causing apparent clinical manifestations, or judged relevant by the investigator, should be reported as an adverse event.

The investigator will provide the following for all adverse events:

1. Description of the event
2. Date of onset and resolution
3. Grade of adverse event
4. Action taken as a result of the event
5. Outcome of event

In this study, descriptions and grading scales found in the NCI Common Terminology Criteria for Adverse Events (CTCAE) version 4.0 available at <http://ctep.cancer.gov> will be utilized for AE reporting.

Investigative sites will report adverse events to their respective IRB according to the local IRB's policies and procedures in reporting adverse events.

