4.1 Recruitment

Patients will be identified from clinical visits to UH Breast Surgery/Hematology-Oncology Clinics and Radiology and the MRI inpatient/outpatient schedules. Patients will be recruited for two different study cohorts:

1. Patients with biopsy proven cases of breast cancer who will undergo chemotherapy treatment. These subjects will receive 3 MRI scans: 1 before chemotherapy, Scan 2 one week to ten days after the first round of chemotherapy, Scan 3 after completion of chemotherapy.
2. The range of scores for MammaPrint is -1 to +1. Any score above 0 is considered low risk. Any patients who have scores 0.355 or above are considered Ultra Low Risk. Patients with biopsy proven cases of breast cancer who have had a low MammaPrint assessment will not be treated with chemotherapy prior to surgery as per clinical standard of care. These subjects will receive only one MRI scan before clinically indicated surgery and/or therapy.

We propose the following pathways for patient recruitment:

- for patients first seen at the Clinics, the treating physician (breast cancer surgeon/breast oncologist) will introduce the study and a flyer with key information about the study may be given to the patient. If the patient shows willingness to participate, the patient's MRN will be sent via UH email to the Radiology Research Coordinator for actual study consent on the day of the baseline diagnostic MRI at UHCMC.
- if the patient has already had a diagnostic scan elsewhere before visiting the Clinic and is still interested in participating in the study, they will be scheduled for a *research only* non-contrast MR Fingerprinting scan at UHCMC before starting chemotherapy.
- alternatively, for patients who are first scheduled for breast MRI at UHCMC Radiology department, consenting will be directly done on the day of MRI without a referral from the breast clinic.

We are requesting a HIPAA waiver to identify eligible patients before approaching them to participate in the study. To confirm study eligibility, we will access the Physician Portal to get information about the breast cancer diagnosis and pathology results.

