4.2 Inclusion/Exclusion Criteria

	Inclusion Criteria:
1.	Biopsy proven cases of breast cancer
2.	Women ages 18 and over

	Exclusion Criteria
1.	Patients with only benign lesion
2.	Patients with only ductal carcinoma in situ (DCIS)
3.	Patients with recurrent/ residual breast cancer in same breast
4.	Pregnant women
5.	Lactating Women
6.	Patients with ferromagnetic or otherwise non-MRI compatible aneurysm clips.
7.	The presence of an implanted medical device that is not MRI-compatible, including, but not limited to: pacemaker, defibrillator
8.	Patients with contraindications for MRI due to embedded foreign metallic objects. Bullets, shrapnel, metalwork fragments, or other metallic material adds unnecessary risk to the patient.
9.	Known history of severe claustrophobia.
10.	Patients under the age of 18
11.	For patients with known history of allergic reaction to MR contrast material or abnormal kidney function (GFR < 40 mL/ min), a contrast enhanced exam will not be performed; however, a non-contrast exam may be performed in these patients.

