9.4 Reporting Procedure for Serious Adverse Event

Serious adverse events that occur beginning with the signing of the informed consent form, or within 30 days of the individual undergoing prostate biopsy must be reported to the University Hospitals Principal Investigator.

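### Sections 9.3 and 9.4 tie safety follow-up to a biopsy and a prostate biopsy that this MRI study of women does not perform, and no end of AE or SAE collection is stated

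*Combined protocol and SAP*

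**What the plan says.** Section 9.3 puts three statements about AE timing in one paragraph:

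- Assessment: "All participating investigators will assess the occurrence of AEs throughout" the subject's time in the study.
- Follow-up: "Subjects will be followed for AEs for 30 days after biopsy or until death, whichever occurs first".
- Recording: the investigator must ensure that all AEs observed or reported "which occur after the subject has signed the informed consent are fully recorded".

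Section 9.4 requires reporting to the Principal Investigator of "Serious adverse events that occur beginning with the signing of the informed consent form, or within 30 days of the individual undergoing prostate biopsy".

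Other sections fix the setting. Section 4.2 requires "Biopsy proven cases of breast cancer" and "Women ages 18 and over". In the clinic pathway of section 4.1, the coordinator is alerted "for actual study consent on the day of the baseline diagnostic MRI at UHCMC"; patients first scheduled through Radiology are likewise consented on the MRI day. Section 4.4.2 lists up to three visits, all MRI. Research gadolinium is possible only at a research-only Visit 3, and section 7.2 describes its risks. For the MammaPrint cohort section 4.1 states: "These subjects will receive only one MRI scan before clinically indicated surgery and/or therapy".

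**The concern.** The two sentences that set a time limit on safety follow-up refer to events that do not fit this trial. A prostate biopsy cannot occur in the enrolled population. The only biopsy relevant to these patients before surgery is the diagnostic one, which took place before they were eligible. The wording appears to have been carried over from a study in which a biopsy was the procedure under observation.

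This is an operative rule, not background text. A coordinator looking for the date on which to stop AE follow-up finds one explicit rule, and it gives a date unrelated to any research procedure. A coordinator looking for the end of SAE reporting finds none. Section 7.2 names allergic reaction and nephrogenic systemic fibrosis as risks of research contrast, so how long to look for events after the last research exposure is a question the protocol needs to answer.

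**Working it through.** The plan gives no figure to reproduce. The check compares sections and then uses day counts to show what the literal rule would do.

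**1. Is there a study biopsy?** Section 4.4.2 has none at any visit. The biopsy date and result in section 5 are items taken from the medical record. Read as a study biopsy, the 9.3 window never starts.

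**2. Read as the diagnostic biopsy, how much follow-up remains after consent?** Let c be the days from diagnostic biopsy to consent. The documents do not give c. Follow-up after consent is max(0, 30 − c):

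| c (assumed) | Days left |
|---|---|
| 7 | 23 |
| 14 | 16 |
| 21 | 9 |
| 30 or more | 0 |

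This applies to both cohorts. Where consent and the single MammaPrint scan fall on the same day, it is also the follow-up after that cohort's only research procedure.

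**3. Where does the window close relative to Visit 3?** Chemotherapy cohort only. Inputs: a course of about 4 to 6 months (section 4.1) and Visit 3 no earlier than the end of chemotherapy (section 4.4.2). Let g be the days from diagnostic biopsy to chemotherapy start (not given, taken as 0 or more). The time from window closure to Visit 3 is at least course length − 30 + g. With g = 0:

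| Days per month | 4-month course | 6-month course |
|---|---|---|
| 28 | 112 − 30 = 82 | 168 − 30 = 138 |
| 30 | 120 − 30 = 90 | 180 − 30 = 150 |
| 30.44 | 122 − 30 = 92 | 183 − 30 = 153 |

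That is roughly 3 to 5 months, and any positive g adds to it. A course stopped early shortens the gap: Visit 3 falls inside the window only if it takes place by day 30 − g after chemotherapy start.

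**4. Can the three statements in 9.3 all be followed?** For a patient who completes all visits, assessment throughout participation must reach Visit 3. The follow-up sentence, with its clause on whichever event comes first, ends before that. The recording sentence has a start (consent) and no end. The paragraph does not say which governs.

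**5. What does 9.4 cover?** Its two limbs are joined by \"or\". The first starts at consent and has no end, so it already takes in every SAE after consent. The second can never apply to a woman. Removing it changes nothing in coverage and leaves the duty with no stated end.

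**6. Is an end stated elsewhere?** Section 10.4 has the coordinator check the EMR for spontaneous AEs, with access for the life of the study. Section 10.7 has a monthly aggregate review and an SAE review within 48 hours. Neither gives a closing date for a patient. Participation is not defined. It might be taken to run to surgical pathology, but that is not written. It would not serve patients who have no surgery, whom section 4.4.2 anticipates, and no end is stated for the MammaPrint cohort.

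**The case against.** The strongest reply is that this is leftover wording with little consequence. Much of that stands, and several stronger readings that a reader might infer are not supported.

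- **That events after research contrast go uncaptured for 3 to 5 months.** They need not. The duty in 9.3 to record observed or reported AEs after consent still applies at Visit 3, as do the EMR check in 10.4 and the monthly review in 10.7. The day counts show how badly the anchor fits; they do not measure lost safety data. They also depend on a reading that the prostate wording in 9.4 makes staff less likely to adopt.
- **That 9.4 misses SAEs.** It does not. The biopsy clause is an extra limb, not an end date. Taken literally, the section over-captures. Even a valid anchor in that sentence would not have supplied an end.
- **That 9.3 holds two incompatible stop rules.** It holds one explicit stop rule, one undefined participation period, and one recording duty with no end. One could read active follow-up and the recording of reported events as cumulative. That would soften the conflict with the recording sentence, but not with assessment throughout participation.
- **That trial results are at risk.** Section 6 plans no AE analysis.

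It is also fair to say that the cancer center monitoring plan (10.7) or local IRB policy (9.3) may already set a period. Neither text is in the documents, so the absence can be asserted only for this protocol. Exposure is limited too: research contrast reaches only patients with no clinical scan within a month of chemotherapy ending, who do not decline it and who meet the eGFR limit. The size of that group is not given.

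**Conclusion.** The point holds in a limited form. Two safety sentences carry anchors that do not fit the study, one of them conflicts with its own paragraph, and the protocol states no end of AE or SAE collection after the last research procedure in either cohort. Confidence is high on the wrong anchors, which are plain on the face of the text, and somewhat lower on the missing end date because the monitoring plan was not available.

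The consequence is operational. Staff cannot derive a correct collection period from sections 9.3 and 9.4 as written. No endpoint, sample size or inference changes. The figure of roughly 3 to 5 months is illustrative. It rests on the diagnostic-biopsy reading, a completed course, and no delay from biopsy to chemotherapy; it does not apply to the MammaPrint cohort, which has no Visit 3. The point should be fixed because an explicit safety rule is wrong and the correction is small.

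**What to change.** Reconcile sections 9.3 and 9.4 with the visits in 4.4.2 and the contrast provisions in 7.2:

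1. Delete both biopsy anchors.
2. State one AE and SAE collection period, from consent to a time set by the sponsor after the last research MRI or research contrast administration, and use it in both sections.
3. Say explicitly that it applies to the chemotherapy cohort and to the single-scan MammaPrint cohort.
4. If the cancer center monitoring plan already sets a period, cite it in 9.3 and 9.4 instead of writing a new one.

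The length of the period is for the sponsor to decide. The cost is an edit to two sentences and a small coordinator workload after the last scan, which can use the EMR review already planned in 10.4.
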